5.10 Storage and Accountability

Records will be made of receipt and dispensing of NE3107 supplied. It is the responsibility of the Sponsor to ensure that storage of study drug is within guidelines of the Investigator's Brochure. It is the responsibility of the Manufacturer to ensure that all drug supplies provided for the study are manufactured under current Good Manufacturing Practices (cGMP) and are suitable for human use.

5.11 Investigational Product Retention at Study Site

Upon completion or termination of the study, all remaining study supplies will be retained according to applicable regulations. Once the retention period has elapsed, any remaining unused drug will be returned to the Manufacturer in the original containers, or destroyed, as directed in writing by the Manufacturer.

6 STUDY PROCEDURES

For this Phase II open label study, all participants will be screened following acquisition of a signed, written informed consent form.

Screening will involve confirmation that all inclusion criteria and none of the exclusion criterion are met. Following confirmation of inclusion and exclusion criterion, participants will undergo baseline testing to include the following: Advanced magnetic resonance imaging (MRI) of the brain, lumbar puncture, APoE genotyping, cognitive testing, and serological analysis.

All patients will have an advanced MRI of the brain to include T1 and T2-weighted structural images, susceptibility-weighted imaging, neuromelanin, arterial spin labeling (ASL) perfusion, blood oxygen level-dependent (BOLD) at rest, diffusion tensor imaging with neurite orientation density and dispersion (DTI-NODDI), and magnetic resonance spectroscopy (MRS) of the precuneus. MRI will demonstrate if patients have tumors, hydrocephalus, subdural hematomas and other structural etiologies of cognitive decline. Having the scan completed will be required for inclusion, but no specific imaging parameters will determine inclusion. The advanced MRI of the brain will be repeated upon completion of the 3-month study intervention period.

All patients will have APoE swab testing and a lumbar puncture for A β 42 and Tau proteins for Alzheimer's Spectrum. This spinal fluid examination has been shown to be both sensitive and specific for Alzheimer's disease. Cerebrospinal fluid (CSF) studies have demonstrated good sensitivity and specificity for mild cognitive impairment (MCI) and dementia of the Alzheimer's type. MRI volumetrics, perfusion scans and MR spectroscopy have shown to be responsive to change as patients progress from MCI to dementia. The lumbar puncture is performed at entry and after completion of the study protocol. The APoE testing will only be performed at baseline.

Baseline and completion (3-month) cognitive testing will include the Quick Dementia Rating System (QDRS), estimated clinical dementia rating (CDR) scale level, Mini-Mental Status Evaluation (MMSE), Montreal Cognitive Examination (MoCA), and Alzheimer's Disease Assessment Scale (ADAS-Cog12). Upon completion of the protocol intervention, participants will also be asked to report a Global Rating of Change (GRC) score in addition to the neuropsychological testing battery.

All participants will be administered the NE3107 and instructed to maintain a consistent daily dosage of 20 mg BID for the three-month active intervention period. Primary endpoints will involve a comparison of neurophysiological health as evaluated by multi-modal brain MRIs and neuropsychological testing obtained at baseline and post-intervention termination (3 months) (See 2.1: *Primary Outcomes* and 2.2: *Secondary Outcomes* for detailed descriptions of the MRI modalities and neuropsychological tests, respectively). Additional procedures include blood and serum samples to be collected at baseline and completion to ensure participant safety and effect of NE3107 on laboratory values (See 6.6.1 *Laboratory Parameters*).

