4.3 Exclusion Criteria

In order for a subject to be considered for this study, he/she may NOT have any of the following:

- Subjects with contraindications for lumbar puncture, such as bleeding abnormalities, use of anticoagulant medications, and local skin or spine abnormalities. *See Section 6.6.1 “Laboratory Parameters,” page 26.*

- Subjects with contraindications to magnetic resonance imaging (MRI) acquisition, including patients with non MRI-compatible pacemakers, defibrillators, or other implanted electronic devices.
- Women who are pregnant, who may become pregnant, or who are breastfeeding
- Reversible causes of cognitive impairment that explains the clinical status entirely, such as hypothyroidism, depression
- Advanced stages of any terminal illness or any active cancer that requires chemotherapy
- History of breast cancer
- Women with child-bearing potential who are not willing to use a double-barrier birth control method
- Males not willing to use a double-barrier birth control method with female sex partners with child-bearing potential
- Individuals with hepatic impairment as defined by:
 - Alanine aminotransferase (ALT) lab values $>3x$ the upper normal limit (UNL)
 - Aspartate aminotransferase (AST) lab values $>3x$ UNLOR
 - History of clinically significant liver disease in the Principal Investigator's medical judgment
- Individuals with renal impairment as defined by Creatinine clearance (Cockcroft-Gault formula) of <45 mL/min.

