Collected at Weeks 2, 4, and 8:

- Amylase
- Lipase
- Potassium
- Calcium
- Complete Blood Count (CBC) with Differential

- Hemoglobin A1c
- Glucose
- Alanine aminotransferase (ALT;
SGPT)
- Aspartate aminotransferase (AST;
SGOT)
- Creatine Phosphokinase
- Cholesterol total (Fasting)
- HDL (Fasting)
- LDL (Fasting)
- Triglycerides (Fasting)

Collected Prior to Lumbar Puncture
Procedure:

- Prothrombin time
- International Normalized Ratio
- Partial thromboplastin time
- Platelet count

6.6.2 *Sample Collection, Storage, and Shipping*

After screening, laboratory orders will be written by the study physician which can be taken to any Quest Diagnostics, LabCorp, or any other clinical laboratory. Additional serum will be drawn at the primary study site and sent for analysis to Prodrome Sciences ([name]). Samples will be shipped on ice and labeled adhering to federal biological substance shipping regulations.

6.7 *Dispensing Study Drug*

The Manufacturer will supply sufficient quantities of the study formulation for the following: (1) completion of this study and (2) retention, as per applicable regulations. All drug supplies provided for this study will be stored in a secure area with restricted access, under controlled storage conditions described in the product package labelling, unless otherwise instructed per protocol.

Records will be made of receipt and dispensing of NE3107 supplied. It is the responsibility of the Manufacturer to ensure that all drug supplies provided for the study are manufactured under current Good Manufacturing Practices (cGMP) and are suitable for human use.

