7 STUDY ACTIVITIES

7.1 Screening Visit & Baseline Measure Collection (Days -10 to -1)

Study Screening may take place during an initial visit with study staff to obtain the following assessments, which will be recorded in participant's source documentation/medical record and on the Case Report Form (CRF):

- Participant ID number generation
- Demographic information
- Medical history
- Vital signs
- Height, weight, and calculation of BMI
- Prior/concomitant medications (must be stabilized for 30 days prior to study entry)
- Quick Dementia Rating Scale (QDRS)
- Clinical Dementia Rating (CDR) score, derived from QDRS
- Confirming eligibility (no exclusionary criteria are met)

Baseline measure acquisition may take place over the subsequent 9 days prior to starting the active study intervention, which will include the following:

- Lumbar puncture to test for AB42 and Tau protein levels
- APoE genotyping
- Advanced brain MRI
 - T1, T2, SWI, Neuromelanin, BOLD, ASL perfusion, DTI-NODDI, MRS of the precuneus
- Cognitive examination including:
 - Montreal Cognitive Assessment (MoCA)
 - Mini-mental Status Examination (MMSE)
 - Alzheimer's Disease Assessment Scale (ADAS-Cog12)
- Blood tests for:
 - Complete blood count + diff
 - Creatinine clearance
 - Thyroid hormone panel
 - Electrolytes
 - Inflammatory markers (hsCRP, TNF α , CD4, CD8, absolute neutrophils)

- Quantitative immunoglobulins
- Total and direct bilirubin
- Hemoglobin
- ProdromeScan blood test for:
 - Phosphatidylethanolamines
 - Choline
 - Mitochondrial function

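### Sections 6, 6.6.2 and 7.1 confirm that no exclusion is met before the study bloods are ordered, so the stated order cannot apply the ALT/AST and creatinine clearance exclusions of Section 4.3

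*Combined protocol and SAP*

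**What the plan says.** Section 4.3 lists ten top-level exclusions. Two set numeric laboratory limits. The hepatic one covers "Alanine aminotransferase (ALT) lab values" above three times the upper normal limit, with the same limit for AST. The renal one is "Creatinine clearance (Cockcroft-Gault formula) of <45 mL/min".

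Three sections then describe when eligibility is decided and when blood is taken:

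- **Section 6** makes screening the step at which all criteria are confirmed, and continues: "Following confirmation of inclusion and exclusion criterion, participants will undergo baseline testing". The baseline testing it lists includes MRI, lumbar puncture and serological analysis.
- **Section 6.6.2** says "After screening, laboratory orders will be written by the study physician".
- **Section 7.1** ends its screening list with "Confirming eligibility (no exclusionary criteria are met". That list holds no blood test. A second list, which holds the blood tests and the lumbar puncture, is introduced by "Baseline measure acquisition may take place over the subsequent 9 days prior to starting the active study intervention".

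Section 7.2 hands out the full three-month supply on Day 0 and mentions no review of results.

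On the other side, Section 6 says of the MRI: "Having the scan completed will be required for inclusion, but no specific imaging parameters will determine inclusion". It also describes "blood and serum samples to be collected at baseline and completion to ensure participant safety". Section 6.6.1 has coagulation bloods taken before lumbar puncture.

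**The concern.** An exclusion defined by a laboratory value can be applied only once the value is known. The plan names one moment at which exclusions are ruled out, and at that moment it has not yet ordered the tests that two of them depend on. Section 6.2 expects recruitment mainly from the investigator's own practice, so earlier chart results may exist, but the plan neither asks for them nor says how recent they must be.

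The stake is participant protection and the integrity of the enrolled population, not the efficacy analysis. Someone whose baseline bloods breach Section 4.3 should not receive drug. If nothing ties the result to entry or dispensing, catching such a person depends on the diligence of whoever reads the report. A secondary stake is the lumbar puncture, an invasive procedure that a person already ineligible on bloods would not need.

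**Working it through.** The plan states no figure on this point. The check is a comparison of sequence, followed by simple dose counts.

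**Order as written**

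| Step | Source | Blood result available? |
|---|---|---|
| Screening visit; exclusions confirmed absent | Sections 6 and 7.1 | No blood test in the screening list |
| Laboratory orders written | Section 6.6.2 | Ordered after screening |
| Baseline bloods, MRI, lumbar puncture | Section 7.1, over the next 9 days | Being obtained |
| Full supply dispensed | Section 7.2, Day 0 | Could be available; no check stated |

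Three sections agree on this order, so it does not rest on one loose sentence.

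**Does another section supply the missing check?**

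- Section 6.9.1 has abnormal values reviewed for safety and lets the investigator end participation because of them. This is a discretionary power, not an entry rule.
- Section 6.11 covers withdrawal, not entry.
- Section 8 reviews laboratory reports for accuracy and completeness, not against Section 4.3.
- Section 7.2 contains no check.

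**Are the tests taken at baseline?** Yes under Section 6.6.1, which lists ALT, AST and creatinine. The Section 7.1 baseline blood list includes creatinine clearance but omits ALT and AST, so the two sections do not match.

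**Share of exclusions affected.** Hepatic and renal: 2 of 10.

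**Next scheduled look if a drawn baseline result is not acted on**

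Inputs: 20 mg twice daily (Section 5.2); treatment Day 1 to Day 90 (Section 7.3); interim panel at weeks 2, 4 and 8 (Section 6.6.1); follow-up at Day 90 ± 15 (Section 7.5).

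- Planned doses: 90 × 2 = 180. Total 180 × 20 mg = 3,600 mg.
- ALT and AST are in the week 2 panel. Doses by then: up to 14 × 2 = 28. Amount: 28 × 20 mg = 560 mg. Share: 28/180 = 15.6%.
- Creatinine is absent from the week 2, 4 and 8 panel; the creatine phosphokinase listed there is a different test. The next scheduled value is at Day 75 to Day 105, with treatment ending at Day 90. Doses by then: 75 × 2 = 150 to 90 × 2 = 180. Amount: 3,000 to 3,600 mg. Share: 150/180 = 83% to 180/180 = 100%.

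These dose counts are a conditional worst case. The documents give no rate of laboratory exclusion, so no number of affected participants can be derived.

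**The case against.** The best defence is that the wording is loose and the safeguard is real. Section 7.1 is one pre-dose block covering Days -10 to -1, and it includes creatinine clearance, the measure that Section 4.3 limits. Section 6 makes a completed MRI a condition of inclusion even though the MRI is itself part of baseline testing, so entry evidently stays open during that period. The lumbar puncture exclusion in Section 4.3 points to Section 6.6.1, where coagulation bloods precede the procedure; the plan therefore does tie at least one exclusion to later tests. Section 4.3 remains the governing rule, so a pre-dose value beyond the limit makes the person ineligible whatever the visit list says. Finally, Appendix 1, the events table, was not available for review and might hold a laboratory draw at screening or a Day 0 check.

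Much of this stands, and it limits what can be claimed. A reader might infer that ineligible people will be dosed. The documents do not support that: bloods come before Day 0, and dosing in breach of Section 4.3 would require a drawn result to be overlooked despite the power in Section 6.9.1. A reader might also infer that the plan puts the lumbar puncture ahead of the chemistry results. It does not; both sit in the same 9-day period with no stated order between them, so an avoidable puncture is possible but not dictated. Nor does the shorter Section 7.1 list show that ALT and AST go unmeasured, since Section 6.6.1 requires them.

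What the defence does not supply is any statement that ALT, AST or creatinine clearance is compared with Section 4.3 before drug is dispensed. The MRI condition concerns completion of the scan, and the coagulation bloods concern a different exclusion. Even if Appendix 1 holds a check, Sections 6, 6.6.2 and 7.1 would still state an order that conflicts with it.

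**Conclusion.** The point holds as a defect in the stated order. Eligibility is confirmed before the bloods that decide 2 of the 10 exclusions are ordered, and no section available for review later ties those results to entry or to dispensing. The renal criterion is the more exposed: if its baseline result is missed, no creatinine is scheduled until Day 90 ± 15, after 83% to 100% of planned doses. For ALT and AST the corresponding figure is up to 15.6%, at week 2. Both figures apply only if a drawn result is not acted on.

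The conclusion rests on the body text of the protocol, on full adherence to twice-daily dosing for the counts, and on the absence of a required prior chart result. Confidence is moderate because Appendix 1 could not be read. This is worth correcting before enrolment: it concerns participant protection, and the correction uses tests already planned.

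**What to change.** - In Sections 6, 6.6.2 and 7.1, state that eligibility is finally confirmed only after baseline ALT, AST and creatinine clearance have been reviewed against Section 4.3.
- In Section 7.2, add a documented check of that review before drug is dispensed.
- Add ALT and AST to the Section 7.1 blood list so that it matches Section 6.6.1.
- Preferably, draw these tests with the coagulation bloods already required before lumbar puncture and review them before the procedure, so that an ineligible person is spared it.
- Check that Appendix 1 agrees.

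The cost is protocol wording and a change in the order of existing tests; no test or threshold is added or altered. The downside is a wait of perhaps a few days for results (an assumption, since the documents give no turnaround time). With the preferred ordering, that leaves less of the 10-day window (Days -10 to -1) for the lumbar puncture and, if it is also held back, the MRI. If the window proves too tight, reviewing the results before Day 0 but after lumbar puncture still closes the dosing gap.

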6.1 Informed Consent

Prior to administration of NE3107, informed consent must be obtained by the participant. The principal investigator, all sub-investigators, and the research coordinator may obtain consent from the subject. All consenting will be done behind closed doors in the privacy of a medical exam room. The participant will be allowed to take home the consent form if he/she needs more time to review the document. The participant will be read the consent form out loud by the member of the study staff obtaining consent. As part of the study criteria, the participant will be required to be cognitively aware and understand the English language. Therefore, the participant's consent should be viewed as their own, and without any undue influence or coercion. If the participant feels uncomfortable, he/she may have an impartial witness of their choice enter the room for the consenting process.

Before signing the consent form, the member of the study staff obtaining consent will verbally ask the participant if he/she has any questions regarding the consent form. If the participant says no, the member of the study staff will ask if all information in the consent form was understood. If the participant says yes, then a member of the study staff will ask if the participant consents to being in this study. If the participant says yes, he/she is ready to sign the consent form.

The principal investigator, all sub-investigators, and the research coordinator may obtain consent from the participant. Once the participant has agreed to be in the study and has signed the consent form, the documentation will exist both physically and electronically. The consent form will be scanned into a computer in which it will be stored under the appropriate folders designated for this research study. The computer will be locked under username, password, and firewall, and will only be accessible by the study staff. The physical version of the consent form will be stored behind lock and key in a drawer or cabinet designated for this research study. The key will also only be accessible by the study staff.

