4.2 Inclusion Criteria

In order for a subject to be considered for this study, the following criterion is required:

- Diagnosis of cognitive decline due to degenerative dementia
- Age within range of 50-89 years old
- QDRS score ranging from 1.5-12.5, with a converted Clinical Dementia Rating (CDR) score of 0.5 (mild cognitive impairment) to 1 (mild dementia)

The QDRS scale will be given to all patients; a cutoff range for QDRS scores has been specified as 1.5-12.5 to qualify patients with a clinical dementia score (CDR) of 0.5 to 1.

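### Consent from participants with up to mild dementia rests on a requirement that is missing from the eligibility lists, with no specified or documented capacity assessment before signature

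*Combined protocol and SAP*

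**What the plan says.** Section 6.1 sets the premise, which it presents as one of the study's criteria: "the participant will be required to be cognitively aware and understand the English language". The next sentence opens with a 'therefore' and says that the participant's "consent should be viewed as their own, and without any undue influence or coercion". Section 10.4 repeats both statements and adds no method of assessment.

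The eligibility lists are elsewhere. Section 4.2 has three entries: a diagnosis of cognitive decline due to degenerative dementia, age 50-89, and "QDRS score ranging from 1.5-12.5, with a converted Clinical Dementia Rating (CDR) score of 0.5 (mild cognitive impairment) to 1 (mild dementia". In 4.3 the one entry about cognition is "Reversible causes of cognitive impairment that explains the clinical status entirely, such as hypothyroidism, depression". On screening, Section 6 says: "Screening will involve confirmation that all inclusion criteria and none of the exclusion criterion are met". The same section places screening after the signed consent.

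For the consent discussion, 6.1 has staff read the form to the participant and ask for questions. If there are none, "the member of the study staff will ask if all information in the consent form was understood". If the answer is yes, the participant is asked to agree and then signs. The principal investigator, any sub-investigator or the research coordinator may conduct this.

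**The concern.** The protocol enrols people because their cognition is impaired, and it expressly includes mild dementia. Whether such a person can weigh the study's risks has to be judged case by case. Sections 6.1 and 10.4 treat the matter as settled by a study criterion, but the lists that define eligibility contain no such criterion, and no section says how it is applied, by whom, or where the result is recorded.

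At stake is whether each participant's agreement to three months of an investigational drug and to lumbar puncture at entry and completion is informed. A person with impaired understanding can answer yes when asked whether everything was clear, and that answer moves the process on to signature.

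**Working it through.** There is no figure to reproduce; the check sets the sections side by side.

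1. **Is the requirement in the eligibility lists?** None of the three entries in 4.2 mentions awareness, capacity or language. Nor does any entry in 4.3, whose cognitive item concerns reversible causes that wholly explain the picture. The description of these requirements as study criteria occurs only in 6.1 and 10.4.

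2. **Who can be eligible?** Under 4.2, anyone from CDR 0.5 to CDR 1 inclusive, so mild dementia is inside the range.

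3. **Does a screening measure come before signature?** No. Section 6 screens after consent is signed, and 10.4 likewise puts consent before screening. The QDRS is a screening item in 7.1, so the plan does not require it before signature. By its description in 9.5.2 it is a caregiver interview that grades impairment; it does not assess the participant's own decision-making.

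4. **Does screening add a check afterwards?** The screening items in 7.1 include demographics, history, vital signs, medications, QDRS and CDR, and confirmation of eligibility. None is a capacity or language step.

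5. **What tests understanding at consent?** Two questions in 6.1: are there any questions, and was everything understood. Both are self-report. No restatement in the participant's own words, capacity instrument or recorded clinical judgement is described, and the coordinator may conduct the discussion without a physician.

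6. **What do the other provisions do?**

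| Provision | Section | Stated to test capacity? |
|---|---|---|
| Form read aloud and may be taken home | 6.1, 10.4 | No |
| Witness, if the participant feels uncomfortable | 6.1, 10.4 | No; doubt about capacity does not trigger it |
| Examination before participation, mainly of the nervous system | 6.3 | No; not tied to signature |
| Earlier records, for patients of the investigator's practice | 6.2 | No |

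7. **Exposure.** Section 9.2 plans approximately 25 participants, and Section 6 plans a lumbar puncture at entry and another at completion: 25 × 2 = 50 planned procedures. This counts what the consent has to cover. It does not estimate how many consents would be unsound.

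**The case against.** The strongest reply is that the protocol is not silent. Sections 6.1 and 10.4 do impose the requirement, so a person who is not cognitively aware fails a written condition of entry. Absence from 4.2 and 4.3 does not prove that a condition is ignored: a completed MRI is required for inclusion under Section 6, and stable concomitant medication is required under 5.6 and 6.10, and neither is in those lists. The wording on screening is not exclusive. A prerequisite for consent may also sit naturally in the consent section. Physicians examine participants before they take part, many will already be known to the practice, and 10.4 binds consent to regulation, good clinical practice and an IRB-approved form. The consent pages were removed from the text reviewed, so a comprehension sign-off there cannot be ruled out.

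Much of this stands. A reader might infer that people with dementia enter with no capacity judgement at all. The documents do not support that: the requirement is stated, and a physician may well judge capacity informally. What remains is that no judgement is specified or documented. The comparison with the other unlisted requirements also has a limit, because 7.1 gives medication stability and the MRI each a place among its procedures and gives none to awareness or English.

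A reader might also infer that the unlisted English requirement undermines the cognitive endpoints. That does not follow. Sections 6.1 and 10.4 do require English, those endpoints are secondary, and they are compared within participant, so a stable language limitation would be present at both visits.

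**Conclusion.** The point holds as an inconsistency with a practical consequence. Two sections rest the validity of consent on criteria that the eligibility lists do not contain, in a population that extends to mild dementia, and the described procedure can be completed on yes-or-no answers without understanding being shown.

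Its size cannot be expressed as a number of participants. A reader might want to combine an assumed share at CDR 1 with an assumed rate of incapacity, but the documents supply neither, and the result would also assume that the stated requirement and the physician's examination exclude nobody. The procedure applies to everyone enrolled, and that is as far as the text goes.

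The conclusion assumes that the removed consent pages contain no capacity or comprehension record. If they do, the missing assessment is partly answered, but the mismatch between 6.1 and 10.4 on one side and 4.2 and 4.3 on the other remains.

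**What to change.** Two changes are needed together.

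- In 4.2, list cognitive awareness sufficient to consent and understanding of English as inclusion criteria, so that the eligibility section agrees with 6.1 and 10.4.
- In 6.1 and 10.4, require the investigator or a sub-investigator to judge the participant's capacity and record that judgement before signature. In place of the yes-or-no question on understanding, have the participant restate the study's purpose, the lumbar puncture risk and the right to withdraw.

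The first change alone is not enough, because eligibility is confirmed only after consent has been signed. The second needs no new staff: 6.9 says that the principal investigator and sub-investigators are medical doctors. If the consent form already carries such a record, 6.1 and 10.4 should refer to it.

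The cost is protocol wording, a few minutes per participant, and possibly a few candidates not enrolled. Section 9.2 says that recruitment is not a limiting factor. Endpoints, sample size and treatment are unaffected.
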